9.4 Methods and Timing for Assessing, Recording and Analyzing Safety Parameters

Hemodynamic safety will be recorded by blood pressure monitoring prior to each administered study dose.

9.5 Adverse Events and Serious Adverse Events

All patients will be evaluated for adverse events (AEs) and serious adverse events (SAEs) routinely at the time of follow-up evaluations. In addition, patients will be instructed to call in with concerns and/or present to their primary care providers. Should concerns for AEs and SAEs be raised, these will then be evaluated further. The time frame of evaluation for AEs and SAEs is confined to the duration of their participation in this study. All events are to be recorded within 1 day of the study team being notified regardless of their relationship to the study intervention and will be adjudicated and classified as outlined below.

For this study, and in agreement with general definitions, an AE is defined as

- Any unfavorable and unintended diagnosis, symptom, sign (including an abnormal laboratory finding), syndrome or disease which either occurs during the study, having been absent at baseline, or if present at baseline, appears to worsen.

A SAE is any adverse event that results in one or more of the following outcomes:

- Death
- A life-threatening event
- Inpatient hospitalization or prolongation of existing hospitalization
- A persistent or significant disability/incapacity
- A congenital anomaly or birth defect
- An important medical event based upon appropriate medical judgment

Date and Time of Onset

The date and time of onset is the date and time when the first sign(s) or symptom(s) were first noted. If the adverse event is an abnormal clinically significant laboratory test or outcome of an examination, the onset date is the date the sample was taken, or the examination was performed.

Classification of AE Severity

The Investigator must grade each adverse event according to the National Cancer Institute (NCI) Common Terminology Criteria for Adverse Events (CTCAE) (version 5.0). According to this guidance document all adverse events are rated on a 5-point scale corresponding to mild, moderate, severe, life-threatening, or disabling and death.

Each adverse event must be graded according to the specific criteria for grading as described in the CTCAE. For events not described in the CTCAE the following criteria will be used:

- Grade 1: Mild; asymptomatic or mild symptoms; clinical or diagnostic observations only; intervention not indicated.
- Grade 2: Moderate; minimal, local, or noninvasive intervention indicated; limiting age-appropriate instrumental ADL*.
- Grade 3: Severe or medically significant but not immediately life-threatening; hospitalization or prolongation of hospitalization indicated; disabling; limiting self-care ADL**.
- Grade 4: Life-threatening consequences; urgent intervention indicated.
- Grade 5: Death related to AE.

Activities of Daily Living (ADL)

*Instrumental ADL refer to preparing meals, shopping for groceries or clothes, using the telephone, managing money, etc.

**Self-care ADL refer to bathing, dressing and undressing, feeding self, using the toilet, taking medications, and not bedridden.

AE Attribution Scale

AEs will be categorized according to the likelihood that they are related to the study intervention as determined by a clinician. The causal relationship can be one of the following:

- 0 = unrelated
- 1 = Unlikely
- 2 = Possibly related
- 3 = Probably related
- 4 = Definitely related

9.6. Reporting Procedure

The reporting system that will be used in this study is summarized in the following table. The study statistician, program manager, and PI will be involved in all data reviews. Any adverse event rate more than twice the expected will be reported to the Mayo Clinic IRB and the study sponsor.

Data type	Frequency of review	Reviewer
Subject accrual (including compliance with protocol enrollment criteria)	Quarterly	Study statistician, Program Manager, PI
Status of all enrolled subjects, as of date of reporting	Quarterly	Study statistician, Program Manager, PI
Adherence data regarding study visits and intervention	Quarterly	Study statistician, Program Manager, PI
AEs and rates (including out-of-range lab values)	Quarterly	Study statistician, Program Manager, PI,
SAEs	Per occurrence	Study statistician, Program Manager, PI, sponsor

SAE

Reporting

SAEs that are unanticipated, serious, and possibly related to the study intervention will be reported by the PI to the IRB, and sponsor in accordance with requirements.

- Unexpected fatal or life-threatening AEs related to the intervention will be reported to the within 7 days. Other serious and unexpected AEs related to the intervention will be reported within 15 days.
- Anticipated or unrelated SAEs will be handled in a less urgent manner but will be reported to the IRB, and sponsor and other oversight organizations in accordance with their requirements.

9.7 Follow-up for Adverse Events

The safety profiles of the study intervention are very well characterized and defined (see above). The rates and outcomes are not expected to deviate from clinical practice and thus this study will adhere to practice standards with assessment of AEs at 24 hours and 90 days.

9.8 Safety Monitoring

The investigator will allocate adequate time for monitoring activities. The Investigator will also ensure that the compliance or quality assurance reviewer is given access to all the study-related documents and study related facilities (e.g., pharmacy, diagnostic laboratory, etc.), and has adequate space to conduct the monitoring visit.

All SAEs will be reported to the IRB according to institutional policy. Screening and application of exclusion criteria will minimize potential risks.

As a service to the investigator, this study may be monitored during the conduct of the trial by staff from the Mayo Clinic Office of Research Regulatory Support. Clinical trial monitoring may include review of the study documents and data generated throughout the duration of the study to help ensure the validity and integrity of the data along with the protection of human research subjects. This will assist investigators in complying with Food and Drug Administration regulations.

10. INTERVENTION DISCONTINUATION

Discontinuation of the study intervention is recommended for any incapacitating and/or life-threatening side effect. Resuming the study medication will depend on an evaluation if the drug can be safely resumed. Patients may have to permanently discontinue study interventions and for this reason participation in this study if intolerable side effects persist.

At any point in time and for any reason, patients may withdraw voluntarily from participation in the study.

In the absence of any reason for premature termination as outlined above, participation will end for every patient after 6 months of trial participation.

Blood pressure will be assessed before administration of the second dose of assigned IV diuretic. In the event of symptomatic hypotension (symptomatic MAP<60 or systolic blood pressure <80 mmHg), the participant will be evaluated by the PI and study team and further dose of study medication will be suspended. The patient, PI and clinical team will be unblinded to allow the clinical team to make a determination of optimal subsequent plans of care and diuretic dosing.

Study stopping rules for safety

We will also implement Bayesian monitoring with utilization of an independent study monitor [name] who will have access to unblinded patient data as they accrue with continuous monitoring of safety. Among the high dose diuretic arm, assuming a probability of serious adverse events of 1/20 (5%) as prior information, we will monitor for 1) symptomatic hypotension (defined above) and 2) a decline in estimated GFR from 0-24 hours of >50%. Based on prior experience with this intervention, we formulated a Bayesian prior distribution for the adverse event rate p associated with this intervention, tantamount to observing 1 adverse event in 20 previous patients, or a 5% prior probability. Based on this prior, the Bayesian prior probability that the true adverse event rate exceeds 20% is only 6%. We have developed a stopping boundary, based on the Bayesian analysis of the accumulating data and the criterion that we would stop the trial if the posterior probability that the true AE rate exceeds 20% gets to 40% or more. This leads to the monitoring boundary at which point, we will pause the study and consider protocol modification and/or cessation of the study as appropriate. This decision will be discussed and made by the PIs from cardiology ([name], [name]) and nephrology ([name]) and statistician ([name])

Posterior probability (%) that $p > 20\%$

Number of AE	1	2	3	4	5	6	7	8	9	10
0	5	4	3	2.8	2.3					

1	15.5	13.5	12.5	10	8.5	7	6				
2		30	27	24	21	18	16	14			
3			46	42	39	35	32	29	26		
4				62	58	54	50	47	43		
5					75						

Based on Mayo observational data, we do not anticipate safety concerns with the high dose diuretic arm. "The recommended use of higher than recommended diuretic dosing for bumetanide is consistent with heterogeneous clinical practice and forms the basis for this prospective study. In our retrospective analysis of 102 patients with severe heart failure admitted to the Cardiac intensive care unit, 28% of patients were receiving very high dose of diuretics (mean dose of 1386 furosemide equivalents administered as bumetanide infusion which would be equivalent to roughly 35 mg of bumetanide administered daily which exceeds the commonly recommended max daily dose of 10 mg of bumetanide which is not based on any data). Very high dose bumetanide compared to conventional therapy (1386 mean furosemide equivalents in 24 hours compared to 257 furosemide equivalents, $p<0.0001$) was not associated with differences in change in mean arterial pressure over the 72 hours of ultra high dose diuretics (mean BP change $2.2 +/- 12.1$ vs $4.1 +/- 12.6$, $p=0.48$) but there was greater loss in weight ($-10.8 +/- 8.7$ vs $-7.2 +/- 8.6$ kg, $p=0.05$) and urine output ($10.0 +/- 4.7$ vs $8.1 +/- 3.8$, $p=0.04$) with no concerning worsening of renal function (creatinine change $-0.03 +/- 0.91$ vs $-0.02 +/- 0.89$, $p=0.81$). It is currently the PI's current practice in the CCU in the last 2 years to use a 12.5 mg bumetanide bolus followed by an infusion at 2 mg/hr (equivalent of 60.5 mg of bumetanide daily) in critically ill cardiac ICU heart failure patients, which has been extremely successful at decongestion with no apparent serious adverse events or untoward hypotension. However, this strategy of upfront high dose diuresis has not been tested with the rigor of a randomized trial forming the basis for this study. The chosen dose of 12.5 mg of bumetanide bid is < half of the currently used diuretic strategy in most CCU patients treated by the PI and many others at Mayo Clinic, Rochester, and a bolus of 12.5 mg of bumetanide has been reported in other studies of heart failure patients [REDACTED]. There remains no randomized data that high dose diuretics are nephrotoxic and the transient changes in renal function observed in clinical randomized trials are reversible and not associated with need for dialysis and are paradoxically associated with better outcomes.³

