Study Product, Dose, Route, Regimen	Patients will be randomized 1:1 to ultra-high dose (IV bumetanide 12.5 mg bid) vs standard dose (IV furosemide as twice the home dose of oral daily diuretic in furosemide equivalents administered bid) for 24 hours. Participants will undergo comprehensive physiological assessment at baseline and 24 hours with short Iohexol clearance for true glomerular filtration rate, apnea hypopnea index, electrocardiography, echocardiography, serum, and urine biomarkers. Patients will be monitored for side effects including muscle cramps, new onset atrial fibrillation (AF), sustained ventricular tachycardia (VT), symptomatic hypotension (MAP<60 or systolic blood pressure <80 mmHg), development of renal insufficiency and dialysis initiation.
Duration of Administration	Patients will be on therapy for 24 hours.

Statistical Methodology	The primary efficacy endpoint is urine output over 24 hours which will be compared by T test between the two groups. Primary safety endpoint will be incident decline in creatinine estimated glomerular filtration rate by 50% over 24 hours. Key secondary endpoints include weight change, NT-proBNP change, urine output, urine sodium excretion, creatinine, and cystatin C estimated GFR changes, apnea-hypopnea index, Iohexol glomerular filtration rate, serum and urine proteomic analyses, peripheral vein pressure and echocardiographic changes over 24 hours, estimated GFR at day 7 or discharge (whichever is sooner) will each be compared by T test between the two groups.
-------------------------	---

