7. STUDY INTERVENTIONS

7.1 Interventions, Administration, and Duration

The ultrahigh dose diuretic arm will receive IV bumetanide 12.5 mg bid for 2 doses total within 24 hours. The standard dose diuretic arm will receive IV furosemide at usual doses (twice the home dose of oral daily diuretic in furosemide equivalents) administered as 2 doses total within 24 hours. Furosemide equivalents will be considered as follows (**40 mg of intravenous furosemide = 1 mg oral bumetanide or 40 mg of torsemide or 80 mg of oral furosemide** consistent with prior literature). There is variability in the reported literature on the conversion from torsemide to furosemide ranging from 1 mg: 1-2 mg conversion for torsemide to intravenous furosemide (JAMA 2023 Jan 17;329(3):214-223). We selected a 1:1 conversion from torsemide to IV furosemide for the standard of care arm to avoid excessively high furosemide doses for those on high doses of home oral torsemide such as 100 mg bid. The determination of diuretic dose for each of the two study drug administrations in the usual care group will be determined as twice the total home daily diuretic dose as IV furosemide split over 2 doses for bid administration. (See table for conversion of commonly used doses) If patients are diuretic naïve, they will be administered 40 mg IV bid if randomized to usual care. This will be the lowest administered diuretic dose in the standard of care arm. Therefore, if patients are on very low oral diuretic doses at home, they will be administered no lower a dose than 40 mg IV bid of furosemide for standard of care arm. The maximum allowable dose of IV furosemide in the standard of care arm will be 100 mg IV bid. Patients will be monitored for side effects including muscle cramps, new onset Atrial fibrillation (AF), sustained Ventricular tachycardia (VT), symptomatic hypotension (systolic BP<80), and dialysis initiation. Following the 2 study drug doses, patients will be subsequently treated by their physicians as per standard of care.

Home dose of diuretic	Study diuretic in standard of care arm
<80 mg of oral furosemide equivalent daily	40 mg furosemide IV bid
80 mg of oral furosemide equivalent daily	40 mg furosemide IV bid

(40 mg of oral furosemide bid or 20 mg torsemide oral bid or 80 mg of furosemide daily or 40 mg of torsemide daily or 1 mg of bumetanide daily)	

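### The section 10 pause rule does not define its counted event consistently, and on the events it lists, death, sustained VT and dialysis do not count in themselves

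*Combined protocol and SAP*

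**What the plan says.** Under the study stopping rules in section 10, an independent monitor with unblinded data follows the high dose arm. The prior and the first monitored event come in one sentence: "assuming a probability of serious adverse events of 1/20 (5%) as prior information, we will monitor for 1) symptomatic hypotension (defined above". In full, the list of events in that sentence is: "we will monitor for 1) symptomatic hypotension (defined above) and 2) a decline in estimated GFR from 0-24 hours of >50" per cent. Hypotension is defined just before as "symptomatic hypotension (symptomatic MAP<60 or systolic blood pressure <80 mmHg".

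The next sentence attaches the same prior to a differently named quantity, the adverse event rate p, "tantamount to observing 1 adverse event in 20 previous patients, or a 5% prior probability". The 40% criterion is written for the true AE rate, and the rows of the table that follows are headed as a number of AE. Neither place says which events are meant.

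Elsewhere the plan names further harms. Section 7.1 lists among the side effects to be monitored "new onset Atrial fibrillation (AF), sustained Ventricular tachycardia (VT), symptomatic hypotension (systolic BP<80), and dialysis initiation". The Study Summary ends a similar list with "development of renal insufficiency and dialysis initiation". Section 9.5 defines seriousness by outcome, starting "A SAE is any adverse event that results in one or more of the following outcomes", and the first outcome on its list is death.

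**The concern.** A Bayesian boundary has meaning only if the prior, the counted data and the threshold all refer to the same event. Here the prior is introduced for SAEs, the count is described as two specific findings, and the threshold is set on an undefined AE rate. These sets differ. A systolic pressure below 80 mmHg or a halved eGFR need not be an SAE under section 9.5, and a death or a sustained VT is neither of the two listed findings. A death before 24 hours also leaves no 24-hour eGFR, so on the listed events it counts only if symptomatic hypotension was recorded first.

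In practice, a monitor faced with a VT, a dialysis start or a death cannot tell from section 10 which row of the table applies. Two careful readers could reach opposite pause decisions on the same data. This is the plan's only numerical trigger for pausing the trial. Section 4.4 intends the safety finding to support a phase III trial, and section 10 acknowledges that the bumetanide doses in its supporting data exceed the commonly recommended daily maximum.

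**Working it through.** **Inputs.** From section 10: prior equivalent to 1 event in 20 patients; prior probability that p exceeds 20% stated as 6%; pause when the posterior probability reaches 40%. From section 1.7 (Sample Size Determination): 10 patients per group.

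**Step 1: reproduce the plan's prior.** Beta(1,19) gives P(p > 0.20) = 1.4%, which does not match. A uniform prior updated with 1 event in 20 patients is Beta(1 + 1, 1 + 19) = Beta(2,20). This gives 5.8%, matching the stated 6%. Its mode is (2 − 1)/(22 − 2) = 5%.

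**Step 2: reproduce the table.** With x events in n patients the posterior is Beta(2 + x, 20 + n − x). All 33 legible cells agree to about 1 percentage point. The largest gap is 1 event in 3 patients (stated 12.5%, computed 11.5%). No gap changes a decision at 40%, so the arithmetic of the rule is sound.

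**Step 3: the boundary.** The posterior first reaches 40% at:

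| High dose patients | Events needed |
|---|---|
| 3-4 | 3 |
| 5-9 | 4 |
| 10 | 5 (4 in 10 gives 39.3%) |

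**Step 4: what the event definition changes.** Suppose the first three or four high dose patients include three who died, had sustained VT or started dialysis, and no patient has a listed event recorded.

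| Data | Listed events only | Those events counted |
|---|---|---|
| 3 such patients in 3 | Beta(2,23): 3.3%, no pause | Beta(5,20): 46.0%, pause |
| 3 such patients in 4 | Beta(2,24): 2.7%, no pause | Beta(5,21): 42.1%, pause |

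With no listed event in all 10 patients the posterior is 0.9%, whatever else has happened.

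**Step 5: illustrative pause probabilities.** The documents give no rates for these events in this population, so the rates below are assumptions. The chance of reaching the boundary within 10 patients was computed exactly, patient by patient. The combined rate is the simple sum if no patient has both kinds of event, and 1 − (1 − a)(1 − b) if the two are independent.

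| Assumed rates (listed + other) | Combined rate | Listed only | All counted |
|---|---|---|---|
| 5% + 5% | 9.75% to 10% | 0.1% | about 1.0% |
| 5% + 15% | 19.25% to 20% | 0.1% | 8.4% to 9.4% |
| 10% + 20% | 28% to 30% | 1.0% | 23.8% to 28.3% |

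Greater overlap than independence would narrow the difference further.

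**Step 6: cost in needless pauses.** If the true rate of the counted event is 5%, the chance of a pause within 10 patients is 0.1%. If a broader definition brings the true combined rate to 10%, it is about 1.0%.

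**The case against.** A reader might infer that death, VT or dialysis can never trigger the rule. The documents do not support that. A patient with one of these events still counts if symptomatic hypotension or the eGFR decline is also recorded, and the undefined AE in the criterion and table leaves a broader count open. A reader might also infer that the prior belongs to SAEs alone, but section 10 goes on to call it an adverse event prior. What stands is the inconsistency, not a proven exclusion.

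The two listed events look deliberate. Section 3.2(a) defines safety by these two findings, and the Study Summary makes the eGFR decline the primary safety endpoint. Monitoring prespecified endpoints formally and handling rare SAEs one by one is a legitimate design. If that is the intention, though, the SAE label on the prior is wrong and the table should say what it counts.

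Other safeguards exist. Section 9.6 has SAEs reviewed per occurrence, unexpected fatal or life-threatening related events reported within 7 days, and AE rates above twice the expected reported to the IRB and sponsor. Section 10 gives an independent monitor continuous unblinded access, and section 13.4 lets the IRB or agencies discontinue the study. Nothing obliges the trial to continue below the boundary. This lowers the stakes. However, section 9.6 gives no expected rate for these harms and ties no pause to its report, and none of these provisions settles what the table counts.

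Finally, a broader count would not catch every serious pattern. Two deaths in the first two high dose patients would give 30% and three in the first five 38.3% (39% in the plan's table), both below 40%. That is correct, and it limits what the change can achieve.

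**Conclusion.** The point holds as an inconsistency in the event definition with a consequence for safety monitoring. Section 10 uses three terms for one rate. On the only events it lists, death, sustained VT and dialysis initiation do not count in themselves. The choice of definition can reverse a decision: 3.3% against 46.0% for three such patients in the first three. That contrast rests only on the Beta(2,20) prior, which reproduces the plan's own figures, and on those patients having no listed event recorded.

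The pause probabilities under assumed rates are illustrations and not estimates for this trial. At low rates the difference is small (0.1% against about 1.0% for 5% plus 5%). It becomes large only if unlisted serious events are common. The prior and boundary calculations are not in error, and the rule is not the trial's only safeguard. This is an inexpensive correction that should be made.

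**What to change.** Reconcile the statements in section 10 so that the prior, the count, the criterion and the table heading all use one definition:

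- Count each high dose patient at most once, if they have symptomatic hypotension, an eGFR decline of more than 50%, death, sustained VT or dialysis initiation. Add treatment-related SAEs if the prior is meant for SAEs.
- State the time window. Section 10 gives 0-24 hours for the eGFR decline only, while sections 8.1.3 and 9.7 describe AE collection over different periods.
- Say how a patient who dies before the 24-hour eGFR is handled; with death in the definition, that patient counts.
- Confirm that 1 in 20 is the prior experience for this definition. If it is not, restate the prior and recompute the table.
- State that the boundary supplements the per-occurrence SAE review in section 9.6 and does not replace it.

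The cost is a few sentences, plus a new table if the prior changes. No new data are needed: sections 7.1, 9.1 and 9.5 already provide for monitoring or recording these events. The statistical cost is the small rise in needless pauses shown in step 6 of the working.
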